6.5 Other Data Collected

Pre-morbid condition

- a. APACHE III Demographics plus history of: hypertension, prior myocardial infarction, congestive heart failure, peripheral vascular disease, prior stroke with sequelae, dementia, chronic pulmonary disease, arthritis, peptic ulcer disease
- b. Survey of smoking history including:
 - Ever smoker (>100 cigarettes in lifetime)?
 - If Yes, current smoker?

- If ever smoker, estimate pack years:
- Pack years = (# packs per day) x (number of years smoked)
- If former smoker, when quit?
- c. Survey of alcohol history (see Appendix O)

6.6 Endpoint Determinations

- 1. Vital status at 28, 60, and 90 days until discharged home on UAB.
- 2. Time of initiation of unassisted breathing (assuming patient achieves 48 consecutive hours of unassisted breathing)
- 3. Need for re-instituting assisted or mechanical ventilation after achieving 48 consecutive hours of unassisted breathing
- 4. Status 48 hours after initiation of unassisted breathing
- 5. Date of ICU discharge
- 6. Date of Hospital discharge

7 Statistical Considerations

Primary Endpoint

The primary endpoint will be ventilator free days. All analyses will be intent to treat. A three-way analysis of variance will be used with factors shown in Table 1. The primary model will be a main effects model. The primary comparisons will be whether initial trophic feeding followed by full-calorie enteral feeding is different than initial advancement to full-calorie enteral feeding.

Table 1: Factorial Design

Factor	Level
	1. Omega-3 Fatty Acid, Gamma-linolenic acid (GLA), and anti-
Nutriceutical (Medical Food)	oxidant supplementation
	2. Placebo
	3. None
Time of Feeding	1. Initial trophic feeding followed by full-calorie enteral feeding
Time of Feeding	2. Initial advancement to full-calorie enteral feeding
Shock at baseline	1. Yes
Shock at baseline	2. No

The maximum sample size will be 1000 patients. The study will be monitored using a flexible group sequential design that stops for efficacy/futility. Since trophic vs. full-calorie feeding is a two-sided question with either strategy possibly improving outcomes, efficacy and futility stopping rules will be the same (i.e. efficacy of one strategy would be the same as futility of the other strategy). The reported confidence intervals on the treatment difference will be adjusted for the group sequential design using the method of Jennison & Turnbull.

In order to allow flexibility we will use alpha and beta spending boundaries as described by DeMets and Ware (zl=2.277,delta=1.663,zu=2.025,m=4, mu=3.3837) (DeMets, 1982). Trophic vs. full-calorie feeding is a two sided question which will have a two-sided efficacy boundary and an inner wedge futility boundary that will be formed by reflecting the lower futility boundary about the abscissa. There would be no chance of futility stopping of two sided factors at the first look.

In this method of interim monitoring we specify a function a(t) and b(t) called the alpha and beta spending functions. The function a(t) gives the amount of the p-value that will be "spent" by a given time "t" in the study, where time runs from 0 at study start to 1 when all patients have been entered. It is the probability under the null hypothesis that the trial will stop for efficacy at or before time t. The function b(t) is the type II error that will be "spent" by the interim monitoring plan to allow futility stopping. It is the probability under the alternative hypothesis that the study will stop for futility at or before time t or that, at the last look, the efficacy boundary will not be exceeded. The reason that we use alpha and beta "spending" functions rather than p-values to stop the trial is that with two co-enrolled trials we may not be monitoring the data of both trials at 250 patient intervals.

Table 2 shows the alpha-spending boundary a(t) where t is the proportion of patients accrued at that DSMB meeting. In the table we have assumed 5 meetings at t= .10, .25, .50, .75 and 1.0 This function a(t) will be extended to a smooth function of t using a cubic spline as suggested by (Pampallona, 1994) and at each DSMB meeting the actual stopping boundary will be calculated so that the probability of stopping at or before that meeting is a(t). Similarly the futility boundary is defined by the beta-spending function b(t). The number b(t) is the cumulative probability that the results would be below the futility stopping boundary given the alternative hypothesis of a 2.25 day increase in VFD with a standard deviation of 10.5. At each DSMB meeting a futility stopping boundary will be calculated so that the probability of futility stopping at or before that meeting is b(t) at this alternative hypothesis.

The overall one-sided significance level of the study will be 0.025 which is equivalent to a two sided p=0.05 significance level. Five analyses are planned after 100, 250, 500, 750, and 1000 patients. Under the assumption that there are five equally spaced interim analyses the power of the study will be 90.7%. Changes in the number or spacing of the interim analyses will have a minor effect on the power. With this design, assuming that the pattern of deaths and extubations is similar to the FACTT fluid study, there is a 82% chance that the study will show both a significant effect of VFD and a nominally positive benefit in mortality.

The DSMB will be advised to consider mortality differences in deciding whether to stop the trial. For example, they might decline to stop the trial for efficacy if the mortality difference would make the positive benefit in ventilator free days difficult to interpret and they might decline to stop the trial for futility if there is a positive mortality benefit. For example, if there was no difference in vent free days but a trend towards a survival benefit the DSMB might continue past a futility boundary. The stopping rules have been set up so that this would not invalidate the trial if such judgments were made. The efficacy boundary has been developed without regard to the futility boundary. Thus if the futility boundary is crossed but the trial is not stopped the trial can still achieve a 0.025 one-sided significance level.

Table 2 shows the characteristics of this boundary if we had the interim reports described above. The second column is the nominal p-value to stop for efficacy; the third and fourth columns are the difference in VFD to stop for efficacy and futility. The next columns are the error spending functions. The type I error spending function is the probability that the upper boundary will be exceeded under the null hypothesis. The type II error spending function is the probability that the statistic will be below the lower boundary at an interim analysis or under the upper boundary at the final analysis under the alternative hypothesis. The probability of stopping for futility is given in the seventh column and the probability of stopping for efficacy in the eighth column. The final column shows the confidence interval for the difference in VFD if the trial stopped for efficacy at that look and the treatment effect just exceeded the stopping boundary.

Table 2: Stopping Boundaries

Number of patients	P-value Efficacy 2-sided	Difference Efficacy	Difference Futility	Type I Error Spending 1-sided	Type II Error Spending	Prob stop futility	Prob Stop efficacy	Confidence interval when no difference
100	1.5 E-6	9.5		7.6E-11	0	0	5E-8	9.3-17.6
250	5 E-5	3.8	-0.50	2.56 E-5	0.0128	0.30	0.009	2.8-8.0
500	0.0042	1.9	0.14	0.0021	0.0232	0.31	0.31	.8-4.5
750	0.0194	1.3	0.35	0.0104	0.0287	0.17	0.41	.3-3.2
1000	0.0429	0.95	0.46	0.0250	0.0923	0.09	0.18	0.0-2.6

Secondary Endpoints

Mortality

Mortality will be compared at interim data analyses using Kaplan Meier estimates at 60 days and their associated standard errors. This analysis will be stratified as above and a test for interaction of treatment with strata will be presented. At the end of the study sixty-day mortality will be compared using a Mantel-Haenzel test as long as all patients can be followed. If not the method used for the interim analyses will be used.

Other Endpoints

The number of ICU-free days, Organ-Failure Free days, and days from first weaning readiness will be analyzed in the same manner as is described above for the primary endpoint. In addition we will test for interactions between treatment and gender and race as per NIH guidelines (National Institutes of Health, 2001).

Changes in plasma levels of IL-6, IL-8, and protein will be compared in two analyses. An analysis of covariance will test for a treatment effect on the day 3 value of these variables using the day 0 value as a covariate. In addition, a multivariate analysis of variance will test for a baseline difference between day 3 and day 0.

Table 3 illustrates the detectable differences for endpoints, assuming 1000 patients enrolled, 90% power, and a two-sided alpha-level of 0.05.

Table 3: Detectable Differences for Secondary Endpoints

Variable	Incidence or Mean	Standard Deviation	Detectable Difference
PaO ₂ / FiO ₂	155	73	15
ICU free days	13.4 days	12.6 days	2.6 days
Shock free days	19.1 days	4.93 days	2.23 days
Plasma IL-6 (pg/ml)	1252	862	177
Plasma IL-8 (pg/ml)	149	93	19
28 day hospital mortality	22%		8.2%
90 day hospital mortality	25.4%		8.6%

Changes in physiologic lung indices on days 1-7 will be compared using a multivariate analysis of variance.

Twice during the early part of the study, the DSMB will evaluate the glucose control between the trophic and full-calorie arms to ensure that the levels of blood glucose are not clinically different between the groups over the first 6 days of the study. These evaluations will occur after approximately 100 and 250 patients are enrolled in the study. Should the blood glucose values differ between the groups at these evaluations, the guidelines for controlling blood glucose levels for the remainder of the study may be adjusted in an attempt to equalize the blood glucose levels for the study.

8 Data Collection and Site Monitoring

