• **Titles:** Prospective, Randomized, Multi-center Trial of Initial Trophic Enteral Feeding Followed by Advancement to Full-calorie Enteral Feeding vs. Early Advancement to Full-calorie Enteral Feeding in Patients with Acute Lung Injury (ALI) or Acute Respiratory Distress Syndrome (ARDS)

• Objectives:

 To assess the safety and efficacy of initial trophic enteral feeding followed by advancement to full-calorie enteral feeding vs. initial advancement to full-calorie enteral feeding management strategies in reducing mortality and morbidity in patients with ALI or ARDS

• Hypotheses:

- 1. Initial trophic feeding followed by full-calorie enteral feeding will improve clinical outcomes (specifically increase the number of ventilator-free days to day 28 and decrease the 60-day, hospital mortality) in patients with ALI or ARDS by reducing systemic inflammation and the number of feeding complications as compared to early, full-calorie enteral feeding.
- **Study Design:** Multi-center, prospective, randomized, controlled clinical trials.
 - 1. A maximum of 1000 patients will be enrolled.
 - 2. Patients randomized to trophic enteral feeds will receive trophic feeding rates (20 kcal / hr) for 144 hours prior to being advanced to full-calorie feeding rates which will continue for the duration of mechanical ventilation up to study day 28.
 - 3. Patients randomized to full-calorie enteral feeds will be advanced to full-calorie feeding rates on initiation of feeding and will continue to receive full-calorie feeds for the duration of mechanical ventilation up to study day 28.
 - 4. Patients will be followed to the earlier of 60 days or hospital discharge. In addition, vital status will be ascertained at 90 days.

• Sample Size/Interim Monitoring:

This study compares the use of initial trophic enteral feeds followed by advancement to full-calorie enteral feeds versus initial full-calorie feeds in patients with ALI or ARDS. The trial will accrue a maximum of 1000 patients providing about 500 patients treated initially with trophic enteral feeds to be compared against about 500 patients treated initially with full-calorie enteral feeds. This provides 90 % power to detect an absolute difference of 2.25 ventilator-free days assuming a mean of 14 and standard deviation of 10.5 ventilator-free days (data from FACTT study) using a two sided p = 0.05 significance level.

- 2 The principal analysis will be intent-to-treat, based upon randomization assignment.

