4.6 Randomization

After obtaining a signed and dated informed consent, the coordinating center will be called and an assignment, in the form of a study ID number, will be made by computer-generated randomization to initial trophic or initial full feedings.

Randomization will be accomplished with a web based randomization system. Each research coordinator will have a unique Personal Identification Number (PIN). The randomization will indicate to study personnel whether the patient is to receive initial trophic or initial full feedings.

The randomization will be stratified by institution, and by shock at study entry to one of the two study arms.

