6.2 Baseline Assessments

The following information will be recorded during the 24-hour interval encompassing the 12 hours prior to randomization and the 12 hours after randomization. If more than one value is

available for this 24-hour period, the value closest to the time of enrollment will be recorded. If no values are available from the 12 hours prior to randomization, then values will be measured during the 12 hours post randomization and prior to initiation of enteral feeds.

- 1. Vital Signs: heart rate (beats / min), systemic systolic and diastolic BP (mmHg), body temperature (⁰C)
- 2. Ventilator mode, rate, minute ventilation, tidal volume, FiO₂, PEEP, plateau, peak, and mean airway pressures
- 3. Arterial pO₂, pCO₂, pH and SpO₂
- 4. Serum electrolytes, magnesium, phosphorous, BUN, creatinine, bilirubin, and glucose
- 5. Blood hemoglobin, hematocrit, WBC, and platelets, Prothrombin time (PT)
- 6. Serum total protein, albumin
- 7. Glasgow Coma Score
- 8. Frontal Chest Radiograph radiographic lung injury score (# of quadrants)
- 9. Administration of the following medications (Y / N):
 - (a) Sedatives
 - (b) Vasopressors
 - (c) Pro-kinetic agents (cisapride, metoclopramide, lactulose, sorbitol, or erythromycin)
- 10. Location of feeding tube (orogastric, nasogastric, oro-enteral, naso-enteral, PEG or jejunostomy tube)
- 11. Presumed site of infection, if sepsis is the etiology of ALI / ARDS
- 12. APACHE III score
- 13. Blood for DNA banking (appendix K)
- 14. Blood for cytokines, mediators, and markers of inflammation. Plasma obtained from two, 10 ml EDTA anti-coagulated blood samples will be divided immediately after centrifugation into 4 equal 2 ml aliquots in specified tubes and frozen at -70° C.
- 15. Urine for F₂- isoprostane metabolites. Urine obtained from the patients will be collected in an 8 ml sample tube and divided into 4 equal aliquots in specified tubes and frozen at 70°C.

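### The primary ANOVA adjusts for shock but omits institution, the other stratification factor, and uses no baseline prognostic measure beyond shock, so the test is mildly conservative and some precision is forgone

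*Protocol*

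**What the plan says.** Protocol section 4.6 names two stratification factors: "The randomization will be stratified by institution, and by shock at study entry to one of the two study arms".

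Protocol section 7, Primary Endpoint, fixes the analysis: "A three-way analysis of variance will be used with factors shown in Table 1", and "The primary model will be a main effects model". Table 1 lists three factors: medical food (three levels), time of feeding (two levels) and "Shock at baseline" (two levels). Institution is not among them. Under Other Endpoints, section 7 sends ICU-free days, organ-failure-free days and days from first weaning readiness through the same analysis.

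Age falls under the demographic data of section 6.1. The baseline list in section 6.2 includes "APACHE III score", "Glasgow Coma Score", arterial pO2 and FiO2. None of these is a term in the primary model.

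The Study Summary says of 1000 patients: "This provides 90 % power to detect an absolute difference of 2.25 ventilator-free days", with a mean of 14 and an SD of 10.5. Section 7 puts the power with interim looks at 90.7% and sets the error rate: "The overall one-sided significance level of the study will be 0.025 which is equivalent to a two sided p=0.05 significance level".

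**The concern.** Stratifying by institution balances the arms within each institution, so differences between institutions contribute little to the variance of the treatment comparison. If the model then ignores institution, those differences stay in its residual variance. The reported standard error is larger than the true one, the confidence interval is too wide, and the test rejects less often than its nominal level under the null.

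The protocol gives reasons to expect institutions to differ. Glucose control follows local practice (5.5), prokinetic use is expected to vary between centres (5.1.7.7), and the feeding site is the medical team's choice (5.1.2).

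The baseline covariates are a separate matter. Age, APACHE III and PaO2/FiO2 are not stratification factors. A model without them has a correct standard error and a correct type I error. It is only less efficient than it could be with data already collected.

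At stake is precision on the primary endpoint and on the day-count secondaries that share its model. Validity in the anti-conservative direction is not at stake.

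**Working it through.** **Inputs.** From the Study Summary and section 7: difference 2.25 VFD, SD 10.5, 1000 patients at 1:1, two-sided alpha 0.05, looks at 100, 250, 500, 750 and 1000. From Table 2: two-sided efficacy p-values 1.5E-6, 5E-5, 0.0042, 0.0194 and 0.0429. The documents give no between-institution variance and no R², so both are assumptions shown as ranges.

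**The plan's own figure.**
- SE of the final difference = 10.5 × √(4/1000) = 0.664. Standardised effect = 2.25/0.664 = 3.388.
- Fixed-sample power = Φ(3.388 − 1.96) = 92.3%.
- Power with five looks was simulated (2 million runs at information times 0.10, 0.25, 0.50, 0.75 and 1.0), using the Table 2 efficacy p-values and the lower futility boundary. With the futility differences exactly as printed it is 90.5%.
- The printed VFD differences are smaller by √2 than the p-values imply. At the last look 2.025 × 0.664 = 1.34, against 0.95 printed, and 0.95 × √2 = 1.34. With the futility differences rescaled by √2, cumulative type II spending is 0.0130, 0.0234 and 0.0288 (tabulated: 0.0128, 0.0232, 0.0287) and power is 90.7%.

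So the stated 90.7% reproduces from the plain SD, with no credit for covariates.

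**Institution balanced but omitted.** Let r be its share of VFD variance. The true SE is 0.664 × √(1 − r), while the model reports 0.664. Then:
- True two-sided alpha = 2 × [1 − Φ(1.96/√(1 − r))].
- Fixed-sample power without institution in the model = Φ((3.388 − 1.96)/√(1 − r)).
- Fixed-sample power with it = Φ(3.388/√(1 − r) − 1.96).

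| Assumed r | True alpha, omitted | Power, omitted | Power, included |
|---|---|---|---|
| 0.02 | 0.048 | 92.5% | 92.8% |
| 0.05 | 0.044 | 92.9% | 93.5% |

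These values assume full balance. Section 4.6 does not describe blocking, and with less balance alpha lies nearer 0.05.

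**Institution and baseline covariates together.** Let R² be the total share of the 10.5² variance that they remove. SE = 0.664 × √(1 − R²). The equivalent in extra patients is 1000/(1 − R²) − 1000. Power is from the same five-look simulation with the effect divided by √(1 − R²).

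| Assumed R² | SE | Fall in SE | Extra patients | Group-sequential power |
|---|---|---|---|---|
| 0 | 0.664 | – | – | 90.7% |
| 0.02 | 0.657 | 1.0% | 20 | 91.3% |
| 0.05 | 0.647 | 2.5% | 53 | 92.1% |
| 0.10 | 0.630 | 5.1% | 111 | 93.3% |

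Two cautions apply. Where institution supplies the R², stratification already delivers part of the gain, as the power columns of the first table show. And shock is already in the model, so R² has to be read as what the new terms explain beyond shock.

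**The case against.** The strongest case against acting has four parts.

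**No stated figure fails.** This stands. The 90.7% was computed without credit for covariates and it reproduces.

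**The covariates are optional.** A simple model that omits age, APACHE III and PaO2/FiO2 is valid, and supportive adjusted analyses are often left to the SAP, which is not shown. This stands as far as validity goes. The institution point is different, because the protocol itself lists the primary factors and so creates the mismatch with section 4.6.

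**The size is undocumented.** This also stands. At a 2% institution share alpha is 0.048 and the SE falls by 1%. The R² of 0.10 needs a contribution from the baseline covariates beyond shock.

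**Changing the model now is not free.** Section 4.1 reports 272 patients already enrolled, which is past the planned looks at 100 and 250. Appendix K.1 refers to 12 study sites, so small samples would be sparse by site. This affects how the change is made. Pooling, or a random effect, deals with small sites.

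A reader might infer more than the documents support. It is not true that the model ignores severity altogether, since shock at baseline is a Table 1 factor. Nor are the standard errors wrong for want of APACHE III, age or PaO2/FiO2; the overstatement concerns institution only. And the trial is not underpowered against its own claim.

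**Conclusion.** The point holds in limited form. Randomisation uses two stratification factors and the fixed primary model carries only one of them. The omission of institution makes inference conservative to the extent that institution is balanced by stratification and predicts VFD. An assumed share of 2% to 5% gives a true two-sided alpha of about 0.048 to 0.044. The omission of baseline measures beyond shock costs efficiency only.

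Taken together, the loss is precision that could be had from data already collected: about 1% to 5% of the standard error for an assumed total R² of 0.02 to 0.10. The omission and its direction can be read from the protocol with confidence. The size cannot, because the documents give neither the between-institution variance nor the prognostic strength of the covariates. The change is worth making, but the trial's validity does not depend on it.

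**What to change.** Amend Table 1 and the primary-model sentence in section 7, without sight of results by arm:

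- Add institution to the main-effects model, either as a random effect or as a fixed effect with small sites pooled by a prespecified size rule.
- Add age, APACHE III and PaO2/FiO2 as prespecified covariates, using pre-randomisation values. This needs saying, because the baseline window in section 6.2 runs to 12 hours after randomisation.
- Use the same model for ICU-free days, organ-failure-free days and days from weaning readiness, and for the interim looks that remain.
- Keep the three-factor ANOVA as a sensitivity analysis.
- State a rule for missing covariate values.

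The cost is a short protocol amendment, the two rules (sparse sites, missing covariates) and reprogramming of the interim statistic. No new data are needed. The power statement can stay as it is, since it claims nothing from covariates.

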- 3 Trial progress will be evaluated by an independent Data and Safety Monitoring Board to determine if the study should stop for futility or efficacy. Interim analyses will be conducted after enrollment of approximately 100, 250, 500, and 750 patients. The study may be stopped if the difference between the numbers of ventilator-free days for the two treatments is greater than the O'Brien-Fleming boundary.
- 4 The DSMB will also monitor the trial for feasibility. Feasibility parameters will include accrual, the ability to follow the enteral nutrition and ventilator protocols, separation of the enteral feeding groups based on volume delivered data. If any of these parameters indicate that the trial is not feasible, the trial will be modified or terminated.
- 5 The trial will also be monitored by the DSMB for safety. Safety parameters will include mortality, vital sign and laboratory data, and adverse event reporting. If any of these parameters indicate to the DSMB that either of the interventions is not safe, the intervention will be modified or terminated.

• Inclusion Criteria

Patients will be eligible for inclusion if they meet all of the below criteria. Criteria 1-3 must all be present within a 24-hour time period:

Acute onset (defined below) of:

- 1. $PaO_2 / FiO_2 \le 300$ (intubated). If altitude > 1000m, then $PaO_2 / FiO_2 \le 300$ x (PB/760)
- 2. Bilateral infiltrates consistent with pulmonary edema on frontal chest radiograph. The infiltrates may be patchy, diffuse, homogeneous, or asymmetric
- 3. Requirement for positive pressure ventilation via endotracheal tube, and
- 4. No clinical evidence of left -sided cardiac failure to account for bilateral pulmonary infiltrates.
- 5. Intention of primary medical team to enterally feed the patient

The 48-hour enrollment time window begins when criteria 1-3 are met. If a patient meets the first three inclusion criteria but has a PAOP (Pulmonary Arterial Wedge Pressure) greater than 18 mmHg, then the first four criteria must persist for more than 12 hours after the PAOP has declined to \leq 18 mmHg, and still be within the 48-hour enrollment window.

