4.1 Number/Source/Screening

The trial will accrue a maximum of 1000 patients over a 3-4 year interval. Approximately 500 patient will be randomized to initial trophic feeding and 500 to initial full calorie feeding. The first 272 patients were enrolled in a 2 x 2 factorial design with an Omega 3 Fatty acid rich medical food versus a control isocaloric medical food. This portion of the trial was stopped by the DSMB for futility.

Patients with ALI or ARDS will be recruited from intensive care units at NIH ARDS Network centers. Study coordinators will visit intensive care units daily to identify potential candidates for enrollment (see inclusion criteria, section 4.2, and exclusion criteria, section 4.3. Permission to approach patients and/or their families will be requested from the attending physicians. All patients meeting the inclusion criteria will be entered on a screening log. If the patient is not enrolled, the screening log will include information explaining why enrollment did not occur (exclusion criteria, attending physician denial, patient refusal, etc. see Appendix L).

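### Table 2's VFD stopping differences are too small by a factor of √2 and its first p-value is too large by 10^4; used as printed, the efficacy differences give about 19% two-sided type I error

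*Protocol*

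**What the plan says.** The Study Summary (Part I, Sample Size/Interim Monitoring) plans the trial "assuming a mean of 14 and standard deviation of 10.5 ventilator-free days (data from FACTT study) using a two sided p = 0.05 significance level", with 90% power for a 2.25-day difference. On allocation, section 4.1 says: "Approximately 500 patient will be randomized to initial trophic feeding and 500 to initial full calorie feeding".

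Section 7 sets the error level: "The overall one-sided significance level of the study will be 0.025 which is equivalent to a two sided p=0.05 significance level". It plans analyses at 100, 250, 500, 750 and 1000 patients, gives the boundary constants as "zu=2.025,m=4, mu=3.3837" (among others), and defines type II spending under "the alternative hypothesis of a 2.25 day increase in VFD with a standard deviation of 10.5". It states power of 90.7%.

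Section 7 then introduces Table 2, in which "the third and fourth columns are the difference in VFD to stop for efficacy and futility". The final column is a confidence interval for an estimate lying just beyond the efficacy boundary. The Study Summary (item 3) also words the rule on the VFD scale: "The study may be stopped if the difference between the numbers of ventilator-free days for the two treatments is greater than the" O'Brien-Fleming boundary.

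**The concern.** Each row of Table 2 gives the same efficacy boundary twice, as a p-value and as a difference in days. The SD and the number of patients link the two, so they must agree, and they do not. At 500 patients the p-value column requires 0.0042, whereas the printed 1.9 days corresponds to p = 0.043. An observed difference of 2.0 days (p = 0.033) would cross the boundary in one column and fall well short in the other.

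These columns are the only thresholds given in clinical units. A DSMB that read them directly could stop the trial, or accept efficacy at the end, on evidence much weaker than the claimed two-sided 0.05.

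**Working it through.** **Inputs.** SD 10.5 and alternative 2.25 days (Study Summary and section 7); about 500 per arm out of 1000 (section 4.1); looks at N = 100, 250, 500, 750 and 1000 total patients; zu = 2.025 (section 7). Section 7 does not write out the formula z = zu/√t. It is inferred from the constant and confirmed in step 1.

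**1. Reproduce the p-value and spending columns.** With t = N/1000, z = 2.025/√t = 6.40, 4.05, 2.864, 2.338, 2.025.
- Two-sided p: 1.5E-10, 5.1E-5, 0.0042, 0.0194, 0.0429. Rows 2 to 5 match the table.
- Cumulative one-sided type I spending by recursive integration: 7.6E-11, 2.56E-5, 0.0021, 0.0104, 0.0250. All five rows match.

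**2. Convert to days.** With N/2 per arm, SE = 10.5·√(4/N) = 21/√N, and the threshold is z·SE.

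| N | SE | z·SE | z·SE/√2 | Printed | Midpoint of printed CI |
|---|---|---|---|---|---|
| 100 | 2.10 | 13.45 | 9.51 | 9.5 | 13.45 |
| 250 | 1.328 | 5.38 | 3.80 | 3.8 | 5.4 |
| 500 | 0.939 | 2.69 | 1.90 | 1.9 | 2.65 |
| 750 | 0.767 | 1.79 | 1.27 | 1.3 | 1.75 |
| 1000 | 0.664 | 1.345 | 0.951 | 0.95 | 1.3 |

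The printed column is z·SE/√2 after rounding. That is what results if each row's N is taken as patients per arm: 2.025 × 10.5 × √(2/1000) = 0.951. The confidence intervals centre on the larger values.

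**3. Check against the stopping probabilities.** Efficacy stopping under 2.25 days at looks 2 to 5:
- corrected thresholds: 0.009, 0.31, 0.41, 0.18, as tabled;
- printed thresholds: 0.12, 0.53, 0.24, 0.07.

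Power with the corrected boundaries and futility stopping is 90.75%, against 90.7% stated.

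**4. Futility column.** Printed values × √2 = -0.71, 0.20, 0.49, 0.65 at 250, 500, 750 and 1000.

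| | Type II spending | Futility stopping under the null |
|---|---|---|
| Table 2 | 0.0128, 0.0232, 0.0287, 0.0923 | 0.30, 0.31, 0.17, 0.09 |
| Printed × √2 | 0.0130, 0.0234, 0.0288, 0.0925 | 0.30, 0.31, 0.17, 0.09 |
| As printed | 0.0192, 0.0269, 0.0297, 0.0953 | 0.35, 0.25, 0.14, 0.08 |

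**5. First p-value.** Twice the adjacent one-sided spend is 2 × 7.6E-11 = 1.5E-10, which is also the p-value at z = 6.40. The printed 1.5E-6 corresponds to z = 4.81. Even the wrong 9.5 days gives 6.1E-6, so nothing in the row explains it.

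**6. Consequence if the printed efficacy differences are applied.** Printed difference/SE gives z = 4.52, 2.86, 2.02, 1.70, 1.43. As a symmetric boundary, the cumulative two-sided type I error is 0.004 at 250, 0.045 at 500, 0.106 at 750 and 0.187 at 1000 (integration and simulation agree). It is 0.179 if the printed futility wedge is also enforced. With the corrected boundary it is 0.050. At the final look alone, 0.95 days has two-sided p = 0.15.

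**The case against.** The strongest reply is that the difference columns are not the operative rule. Section 7 says the boundary is computed at each meeting so that cumulative stopping probabilities equal the spending functions, and Table 2 only illustrates one assumed schedule. The type I spending column is correct in every row, so a DSMB following that text keeps the 0.05 level. This stands, and it makes the 19% conditional on applying the printed differences.

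Second, the 19% includes misuse at the final analysis, which section 7 describes as an analysis of variance and not as a cut-off in days. If the printed differences were misused at the four interim looks only, with z = 2.025 at the end, the error is about 0.116. That also stands; it is still more than twice the intended level.

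Third, the summary's stopping sentence names the O'Brien-Fleming boundary and not the day column of Table 2, so it supports direct use of that column only weakly.

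Fourth, the futility error cannot inflate type I error, because the efficacy boundary was built independently of it. At 250 a negative value produces no inner wedge whether it is -0.50 or -0.71, and at 1000 the efficacy boundary decides. The practical effect is at 500 and 750. The wrong first p-value is also harmless in itself: using z = 4.81 at the first look leaves overall error at 0.050.

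None of this makes the columns right. Section 7 defines them as the differences at which to stop and nowhere warns against using them. An SD of 7.4 or 1000 patients per arm would reproduce them, but both contradict the stated inputs and would give power of 99.8%.

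**Conclusion.** The error is real and should be corrected. Both difference columns of Table 2 are too small by √2, and the first p-value is too large by a factor of 10^4. The result rests only on the protocol's own SD of 10.5, 1:1 allocation, looks counted in total patients, and the O'Brien-Fleming form that the table's p-values confirm. Applied at every look, the printed efficacy differences give two-sided type I error of 0.187 against 0.05. The recalculation rule in section 7 lowers the chance of this happening but leaves two conflicting efficacy thresholds in each row.

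**What to change.** In Table 2:
- replace the efficacy differences by 13.4, 5.4, 2.7, 1.8 and 1.34 days;
- multiply the futility differences by √2, giving -0.71, 0.20, 0.49 and 0.65 days at 250, 500, 750 and 1000, before reflecting them into the two-sided wedge;
- change the 100-patient p-value to 1.5E-10.

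Add one sentence saying that the z/p boundary from the spending functions governs, and that the differences in days are derived from it at SD 10.5 for the assumed looks.

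The cost is one table correction and a note to the DSMB. Sample size, look schedule, spending functions and power are unchanged.
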